Study Protocol

Official Title: Can Blocking the Orexin System Enhance Sleep's Benefits to Therapeutic Exposure for PTSD?

NCT number: NCT02849548

Date of the Document: July 7,2016

Approach

Study Team: The highly qualified interdisciplinary study team has significantly contributed to the proposal and will continue to guide the candidate. [name]., primary mentor, is an expert in sleep, PTSD, and pharmacological trials for PTSD and insomnia and advises on all aspects of the clinical trial. [name]., co-mentor, contributes his expertise in neurophysiology and animal models of PTSD and sleep and advises on all aspects of the animal pilot study. [name]., co-mentor, contributes his expertise in neurophysiology and optogenetic methods and supervises the implementation of the animal pilot study. [name]., collaborator, contributes his expertise in biostatistics. [name]., consultant, contributes his expertise in optogenetic manipulations of orexin neurons using transgenic mice.

Clinical Study Approach: AIM 1: To examine effects of pharmacologically blocking the orexin system after WNE on sleep, PTSD symptoms, and intersession habituation.

Participants: Participants will be physically healthy adults (1:1 gender ratio) (age 18 – 55) who meet DSM-5 criteria for PTSD⁵⁷ with index trauma exposure within the previous 5 years. Justifications for this include a greater likelihood of remembering the details of the event and our prior finding indicating changes in sleep characteristics over the duration of PTSD.⁵⁸ Exclusion criteria include: 1) medical or psychiatric conditions that require consistent use of medication, except for hormonal contraceptives; 2) medical condition that affects sleep; 3) inability to remember most details of the index event; 4) body mass index ≥ 40 (due to very high comorbidity rates of sleep apnea⁵⁹); 5) diagnosis of a sleep disorder other than insomnia including PSG findings of apnea/hypopnea index $> 10/\text{hour}$; 6) consumption of more caffeine than 5 cups of coffee/day equivalent; 7) smoking > 20 cigarettes/day; 8) habitual bedtimes after 2AM, habitual rise times after 9AM, or habitual napping > 1 hour/day; 9) moderate or severe alcohol or drug use disorders within the past year; 10) positive urine toxicology for illicit drugs including cannabis; 11) a diagnosis of psychotic disorders, bipolar disorder, or depression that preceded the onset of PTSD; 12) suicidal ideation with intent to act or with specific plan and intent in the past 6 months [Type 4 – 5 ideation on the Columbia Suicide Severity Rating Scale (C-SSRS)] or history of a suicide attempt; 13) completion of exposure-based therapy targeting the index trauma; 14) pregnancy or breast feeding (All female participants will be required to complete an urine pregnancy test. Sexually active female participants will be required to use a medically acceptable form of birth control); 15) known sensitivity or allergy to an orexin receptor antagonist; and 16) limited ability to read or write English.

Design and Overview (Table 3): This is a randomized, double-blind, placebo-controlled trial examining the effects of suvorexant (Merck & Co., Kenilworth, NJ), a dual orexin receptor antagonist that is FDA approved for insomnia, on sleep and PTSD symptom reduction following WNE. We will employ our successful recruitment strategies, including flyers, outreach activities, and referral from previous participants. Potential participants will initially be screened over the phone or in person, and those who meet initial criteria will be invited to the Clinical Research Unit (CRU) at Howard University to complete a consent procedure, questionnaires, a clinical interview, a physical examination, and urine tests. Participants who meet the selection criteria will be invited to complete two pairs of 30-minute WNE sessions and four overnight PSG recordings [screening, baseline, between WNE sessions (twice)]. Both pairs of WNE sessions will occur at 8PM and 8AM in the following morning with intervening sleep. The second pair will occur one week after the first pair. Four WNE sessions are

Table 3. Study Design

Day	1	2	3	4	5	11	12	18
Consent; Questionnaires	X							
Physical exam	X							
Vital signs	X				X		X	
Urine tests	X							
CAPS (lifetime & past month)	X							
SCID	X							
CAPS (past week)				X	X		X	
C-SSRS	X			X	X		X	
Alertness scale				X	X		X	
Adverse event assessment	X			X	X	X	X	
WNE (AM)					X		X	
WNE (PM)					X		X	
Suvorexant or placebo					X		X	
PSG		X screen	X baseline		X		X	

needed because the majority of participants in the preliminary study did not achieve remission until after completing the second pair of WNE. Participants will be stratified by gender and randomly assigned to either suvorexant or placebo. After the 1st evening WNE, a 10 mg tablet of suvorexant or placebo will be administered orally 30 minutes before bedtime. If the medication is well tolerated, the dose will be increased to 20 mg at the 2nd administration after the 3rd WNE. The recommended dose is 10mg, and the maximum recommended dose is 20mg.⁶⁰ The 1-week CAPS will be administered before the 1st and 3rd sessions and at 1-week follow-up.

Feasibility: The primary mentor's lab has been successfully recruiting, on average, one trauma-exposed participant/week. A pilot study will be conducted during the current KL2 to address potential barriers for recruitment and retention of participants. In the R21 funded study, approximately a half of participants met inclusion criteria and completed at least first two WNE sessions (Fig. 2). Therefore, we expect to enroll 140 participants during the 40-month K01 recruitment period (3.5/month), and ~70 of them would complete at least first two WNE sessions. Based on the previous retention rate, we estimate that 54 participants (27 in each group) would complete the entire protocol. Reasons for dropouts from the R21 study included time conflicts and a family emergency. No participants reported distress related to WNE as a reason for withdrawal.

Assessment: Screening and self-report measures. The initial phone screening will include questions about excluded conditions, trauma exposure, and PTSD symptoms (using the Primary Care PTSD screen,⁶¹ a 4-item screener). The questionnaire package includes a demographic questionnaire, the Life Event Checklist (LEC)⁵⁵ to determine the most stressful event (the index trauma), and a sleep questionnaire developed in the mentor's lab to assess habitual sleep schedule and signs of possible narcolepsy.

Medical/physical tests. Vital signs, height, and weight will be measured, and a physical examination will be performed by a physician or a nurse practitioner. Urine toxicology screening (all participants) and a urine pregnancy test (all female participants) will be conducted by a nurse at the CRU.

Clinical interviews. Structured interviews will be conducted by clinically trained staff and will be reviewed weekly in a consensus conference with the candidate (a licensed psychologist) and the primary mentor (a board certified psychiatrist). The CAPS⁵⁵ will be administered to assess current (past month and past week) and lifetime PTSD diagnosis and severity associated with the index trauma. The Structured Clinical Interview for DSM-5 (SCID)⁶² will be administered to assess current and lifetime psychiatric diagnoses and confirm inclusion criteria. The C-SSRS⁶³ will be administered at the initial visit to assess suicidal ideation and behaviors in lifetime and past 6 months and at subsequent visits to assess any changes since the previous visit. The PI will be immediately notified if a participant indicates concerning suicidal ideation or behaviors.

Sleep recordings. PSG recordings in the CRU will use a Natus/Embla (Pleasanton, CA) Titanium PSG unit including two central, frontal, and occipital EEG leads, two electrooculograms, chin and limb electromyograms, and an electrocardiogram. Participants will be instructed to go to bed at their habitual bedtime and wake up at 8 AM. Screening for sleep disordered breathing will be performed using the screening night data. Visual scoring of sleep records will be done following the American Academy of Sleep Medicine Manual, Version 2.3.⁶⁴ We will calculate standard PSG sleep parameters including total sleep time, WASO, the percentage and the duration of each sleep stage, and REM density using the REMLogic software (Natus/ Embla). Sleep changes from baseline to post-WNE will be computed by subtracting baseline measures from respective measures obtained during sleep following the 1st and 3rd WNE sessions.

Alertness visual analogue scale (VAS). Participants will complete an alertness VAS upon awakening in the morning after PSG recordings. The VAS is a 100 mm horizontal line with a label "very sleepy" on the left end and "very alert" on the right end. Participants will be place a

slash mark on the scale to indicate their alertness at the moment. A morning WNE session will not begin until the participant's alertness level reaches the level he/she indicated in the morning after the baseline PSG recording.

Adverse event assessment. Participants will be queried regarding the presence of any symptoms or concerns before and after the medication administration.

Pulse rate. The pulses will be continuously recorded during the 5-min baseline and the 30-min WNE through a finger pulse transducer of the PowerLab system (ADIInstruments, Colorado Springs, CO). Data will be visually inspected using the LabChart software (ADIInstruments), and segments with artifacts will be excluded. The average pulse rates for the 5-min baseline and each 2-minute epoch during WNE will be computed. A baseline-corrected highest average pulse rate for each session will be computed by subtracting the session's average baseline pulse rate from the highest average pulse rate in the session. The baseline correction will be performed to correct for circadian influences on pulse rates.⁶⁵⁻⁶⁷

Study Medication: Suvorexant, a dual orexin receptor antagonist, is the first and only FDA-approved agent in this class for treatment of insomnia. Over 2,000 patients with insomnia have been exposed to suvorexant in one 4-week Phase IIB, two 3-month Phase III, and one 1-year Phase III trials.^{48,49,68} Suvorexant (both 10 mg and 20 mg) reduced PSG-measured WASO and increased total sleep time, sleep efficiency, and REM sleep on the first night and at 4-week follow-up. In the largest trial, 20 mg (non-elderly)/15 mg (elderly) suvorexant increased SWS on the first night in patients with insomnia, and the effect was greater with a higher dose, 40/30 mg.⁵⁰ No gender differences were found in its effects on self-reported or PSG outcomes or its safety.^{48,60,69} The most common adverse effect was somnolence which occurred in 7% of insomnia patients receiving 20/15 mg, daily for 3 months compared with 3% receiving placebo. Other adverse events included nasopharyngitis (5%) and headache (7%), although these rates were comparable to the rates for those receiving placebo. Only 3% of the 3-month trial participants receiving suvorexant discontinued treatment due to adverse effects, which was comparable to the rate for those receiving placebo. The recommended dose is 10 mg, once daily, and the maximum recommended dose is 20 mg. The prescription information provided by Merck instructs to take the medication within 30 minutes of going to bed and stay in bed for at least 7 hours.⁶⁰ Given that suvorexant's effects on SWS were stronger with the higher doses, in this study, the dose will be increased from 10 mg at the 1st administration to 20 mg at the 2nd administration if the participant tolerated the lower dose well. The 2nd dose will remain at 10 mg if the participant had mild to moderate sedation in the morning after the 1st administration. If the participant had significant adverse events (that is rare), he/she will not have the 2nd administration. The CRU nurse and the study staff will monitor participants' alertness level in the following morning, and those who remain at a low alertness level will be prohibited from driving themselves.

Study Medication Administration: Participants will be stratified for gender and randomly assigned to either suvorexant or placebo before the 1st WNE. Suvorexant or placebo will be administered orally after the 1st and 3rd WNE, 30 minutes before the participant's habitual bedtime. If the participant well tolerates 10mg, the dose will be increased to 20mg at the 2nd administration. Participants will have continuous access to research nurses during the sleep recording. In the following morning, a nurse will assess possible adverse effects.

Written Narrative Exposure (WNE): We will use a procedure similar to the one used in the R21 study. Sessions will begin at 8PM and approximately 8AM. The morning sessions will not start until the participant's alertness level reaches the level he/she indicated in the morning after the baseline PSG recording. The participant will sit at a desk in a private room with a facilitator, and a pulse transducer will be attached to the distal of the middle finger of his/her non-dominant hand placed on the desk. After a 10-minute acclimatization period, a 5-minute baseline pulse recording will begin. At the end of the baseline, the facilitator will provide instructions to write in as much detail as possible about his/her index trauma including what

happened, how s/he felt, and what s/he perceived and thought and to use the entire 30 minutes. The facilitator will also instruct the participant to orally report an overall level of distress on a scale from 0 – 100 [subjective units of distress scale (SUDS)] at baseline, every 10 minutes, and at the end of the writing period. The facilitator will remain in the same room during the writing to obtain SUDS scores and to assist and encourage the participant if necessary. At the end of the writing period, if warranted, the facilitator will instruct the participant in relaxation techniques for ≤10 minutes. Participants will not be dismissed until distress is minimal.

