Power considerations. G*Power⁷¹ was used to perform power analysis. $\alpha = .05$ was applied in all analyses. We estimate that 54 participants (27 in each group) will complete protocol (see the Feasibility section). **Hypothesis 1a:** The primary outcomes for power evaluation are WASO and REM sleep. The prior studies suggest small effects of suvorexant on N3; therefore, it was not considered for power evaluation. Herring et al's clinical trials^{48,50} showed that effect sizes of one night of 20/15mg suvorexant on WASO and REM sleep (minutes and %) were $f = -0.37$, 0.32, and 0.22, respectively. A total of 16, 22, and 50 participants are needed to detect a Group x Time effect on WASO and REM sleep in minutes and percentage, respectively, with 80% power. Since no studies have examined effects of suvorexant on PTSD, power analysis for **Hypothesis 1b** is based on effect sizes found in Taylor et al's⁴⁴ clinical trial of prazosin in civilian outpatients with PTSD. 12 participants are needed to detect the effect size found in this trial ($f = 0.40$). **Hypothesis 1c:** Sizes of the indirect effects of suvorexant on PTSD and intersession habituation through post-WNE sleep change are unknown. We selected the bootstrapping procedure as it is more powerful than Sobel test.⁷²

The proposed study also includes comparisons of several other variables. The relative sample size required for multiple comparisons of variables (between 10-20) allowing for Bonferroni-adjusted test to achieve 80% power relative to the sample size required for a nominal is only 3.⁷³ The proposed sample size of 54 will, therefore, have adequate power to detect medium to large effects in our planned analyses. Statistical significance of effects and their clinical importance will be carefully considered in data interpretation to inform the development of subsequent grant applications.

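### Past-week CAPS has no provision for people who stop attending, so Hypothesis 1b would by default compare completers, losing about 16 of the 70 who finish Session 2

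*Protocol*

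**What the plan says.** **When CAPS is taken.** The protocol's Design and Overview section states: "The 1-week CAPS will be administered before the 1st and 3rd sessions and at 1-week follow-up". Timing here is taken from that sentence, because the columns of Table 3 are not reliable in the text version.

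**When drug starts.** Study Medication Administration: "Participants will be stratified for gender and randomly assigned to either suvorexant or placebo before the 1st WNE". Design and Overview: "After the 1st evening WNE, a 10 mg tablet of suvorexant or placebo will be administered orally 30 minutes before bedtime", and, for the later sessions, "The second pair will occur one week after the first pair". The earliest CAPS after drug is therefore the one before Session 3, about a week after the first dose.

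**Expected flow.** The Feasibility section expects 140 enrolled and about 70 completing at least Sessions 1 and 2, and then "we estimate that 54 participants (27 in each group) would complete the entire protocol". On the previous study it says: "Reasons for dropouts from the R21 study included time conflicts and a family emergency".

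**Stopping drug.** Under Study Medication, a participant with significant adverse events, described there as rare, is covered by the rule that "he/she will not have the 2nd administration". The section does not mention that person's later assessments.

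**Analysis.** The SAP's Data Analysis Plan tests the Group by Time interaction on CAPS with a repeated-measures ANOVA. It gives no analysis population and no rule for missing scores. Power considerations works from the same projection: "We estimate that 54 participants (27 in each group) will complete protocol".

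**The concern.** Randomisation and the first dose both come before the first opportunity to lose a post-drug CAPS. A participant who is dosed, completes Sessions 1 and 2 and does not return leaves only a pre-drug score. One who attends for Session 3 and then stops leaves one post-drug score out of two. Nothing in either document asks for the missing interviews.

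Two gaps then compound. The first is in collection: an outcome never obtained cannot be recovered by any later choice of model. The second is in analysis: a classical repeated-measures ANOVA needs all three scores from each person, so even those with one post-drug CAPS drop out unless the SAP says otherwise.

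At stake is whether the CAPS comparison describes the groups as randomised or those who stayed to the end. The same missing scores would be absent from the Hypothesis 1c path analysis on PTSD, although many of these people would have the sleep recording between Sessions 1 and 2. The pulse-rate comparison between Sessions 1 and 2 is not affected in this way and could use all of the roughly 70.

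**Working it through.** **1. The plan's flow figures (Feasibility)**
- Enrolled: 40 months × 3.5 per month = 140.
- Through Session 2: 140 × about 0.5 = 70.
- Full protocol: 2 × 27 = 54. The earlier retention rate behind this figure is not given, so it cannot be derived independently.

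**2. Losses after Session 2**
- 70 − 54 = 16, and 16/70 = 22.9%.
- If x of the 16 leave before the Session 3 visit, x have no post-drug CAPS and up to 16 − x have one. The documents do not give x, so the range is 0 to 16.
- The 70 are people who finish Session 2, not everyone dosed. If 75 or 80 were dosed (assumed), non-completers would be 75 − 54 = 21 (28%) or 80 − 54 = 26 (32.5%).

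**3. Does the plan's CAPS sample size assume all three scores?**

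The SAP says 12 participants are needed at f = 0.40. For a within-between interaction with 2 groups and m time points, λ = f²·N·m/(1 − ρ), with df1 = m − 1 and df2 = (N − 2)(m − 1). The documents do not give ρ or the sphericity factor; 0.5 and 1 are assumed, with α = 0.05 and 80% power.
- m = 3: λ = 0.16 × 12 × 3/0.5 = 11.52, df 2 and 20, power 0.81. This reproduces N = 12.
- m = 2: power at N = 12 is 0.705, and N = 16 would be needed.

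Under these assumptions the stated 12 fits an ANOVA using all three CAPS, which is the model that loses anyone with a gap.

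**4. Possible bias**
- Let δ be the drug effect in completers, with losses equal by arm (8 of 35 in each, as 27 per group implies). If leavers have the same effect δ, the bias is zero.
- If leavers have no drug effect, the difference across all 70 is (54/70)δ, so the completer difference overstates it by 70/54 = 1.30.
- In SD units, if one arm's leavers differ from that arm's completers by 0.25 to 1.0 SD (assumed), the group difference shifts by 8/35 × 0.25 = 0.06 to 8/35 × 1.0 = 0.23 SD.

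**5. Precision**
- Standard error with all 70 relative to 54: √(54/70) = 0.88, about 12% smaller.
- With half of the 16 recovered (n = 62): √(54/62) = 0.93, about 7% smaller.
- Detectable f at 80% power (m = 3, ρ = 0.5) falls from 0.175 at 54 to 0.153 at 70. At f = 0.40 power exceeds 99% either way.

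**The case against.** The strongest reply has four parts.

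**The SAP never says completers only.** This is correct. The 54 is a feasibility and power projection, and a reader might wrongly take it as a declared analysis set. The completer analysis is an inference from the named ANOVA and the silence on missing scores. That silence still leaves listwise deletion as the default.

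**Loss may be unrelated to outcome.** The dropout reasons reported from the R21 study concern scheduling and family, and the Feasibility section adds that nobody there withdrew because of distress from the writing sessions. This supports the no-bias end of the range. It does not settle the matter, because it comes from an earlier study and not from this comparison of suvorexant with placebo.

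**Selection on drug tolerance is not shown.** A reader might infer that the adverse-event rule removes suvorexant participants from the CAPS analysis, leaving only those who tolerated the drug. The documents do not support this. The rule withholds the second administration, which on the schedule follows the pre-Session 3 CAPS, and it cancels no CAPS. Study Medication also reports 3% discontinuation for adverse effects in 3-month trials, comparable to placebo. Applied to an assumed 35 per arm that is 0.03 × 35, about one person, and exposure here is at most two doses. What remains is that the protocol does not say these participants stay in CAPS follow-up.

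**Power is ample.** At the planning effect it is, so lost precision is secondary. The main issue is whom the comparison represents.

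**Conclusion.** The point stands as a gap in outcome collection and in the analysis rule. On the plan's own figures, about 16 of the 70 who finish Session 2 (23%) would lack part of the protocol. Anyone missing a CAPS score as a result would by default be left out of the Hypothesis 1b CAPS analysis. People dosed who leave before Session 2 are additional.

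Two stronger statements should not be made. It is not established that all 16 would lack any post-drug CAPS; the number is between 0 and 16. Nor is a 30% overstatement the expected bias. It is the extreme under two assumptions: no leaver benefits from drug, and losses are equal by arm. If leavers resemble completers there is no bias, only a standard error that full recovery would make about 12% smaller.

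This is a worthwhile, inexpensive improvement: missing interviews cannot be obtained afterwards, and the size and direction of any bias could not be checked from completers alone.

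**What to change.** **Protocol, Design and Overview.** State that the pre-Session 3 and 1-week follow-up past-week CAPS will be sought at their scheduled times from every randomised participant who has not withdrawn consent, whether or not sessions or study drug continue, and by telephone if the participant does not attend. Record the interview mode. Say explicitly that this includes anyone who does not receive the second administration. This concerns outcome collection only and changes no treatment rule.

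**SAP, Hypothesis 1b.** Analyse CAPS for all randomised participants by assigned arm, using a likelihood-based mixed model for repeated measures that keeps people with incomplete scores. Report the completer ANOVA as a sensitivity analysis. Both changes are needed: the model cannot supply post-drug scores that were never collected, and collecting them helps less if one remaining gap still removes the person.

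**Cost.** A short addition to each document, and at most about 16 × 2 = 32 telephone interviews for losses after Session 2 over the 40-month recruitment period. There would be up to two more for each person lost between randomisation and Session 2, so 32 is not a ceiling. The existing trained interviewers could do them. The downside is mixed interview mode, with telephone scores concentrated among those who stopped attending. That leavers would usually agree to an interview is a judgement, not something the documents show. No extra participants or visits are needed.

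### Minor: participants who go to bed after 1 AM would get less than the cited seven hours in bed on dosing nights

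*Protocol*

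**What the plan says.** Four parts of the Protocol bear on this.

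- **Participants, exclusion 8** rules out "habitual bedtimes after 2AM, habitual rise times after 9AM, or habitual napping" of more than an hour a day. A bedtime of exactly 2 AM is therefore eligible.
- **Assessment, Sleep recordings:** "Participants will be instructed to go to bed at their habitual bedtime and wake up at 8 AM". This covers every recording night, dosed or not.
- **Study Medication Administration:** suvorexant or placebo "will be administered orally after the 1st and 3rd WNE, 30 minutes before the participant's habitual bedtime".
- **Study Medication** reports that the manufacturer's prescribing information "instructs to take the medication within 30 minutes of going to bed and stay in bed for at least 7 hours".

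The Protocol also has safeguards. Under Study Medication Administration, "Participants will have continuous access to research nurses during the sleep recording". Under Study Medication, the dose rises from 10 mg "to 20 mg at the 2nd administration if the participant tolerated the lower dose well". Otherwise, "The 2nd dose will remain at 10 mg if the participant had mild to moderate sedation in the morning after the 1st administration", and a significant adverse event cancels the second dose. In the morning, "those who remain at a low alertness level will be prohibited from driving themselves". Under Written Narrative Exposure, the morning session starts at about 8 AM and waits until alertness is back to its level on the morning after the baseline recording.

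Neither document sets a minimum time in bed or a different bedtime or wake time for dosing nights.

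**The concern.** The cited instruction has two parts: when to take the tablet, and how long to stay in bed afterwards. The dosing schedule is consistent with the first part. Nothing secures the second, and no reason is given for leaving it open. The latest eligible bedtime and the fixed wake time together allow a shorter night than the instruction describes.

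Exclusion 8 also admits usual rise times up to 9 AM. Someone who normally sleeps from 2 AM to 9 AM has seven hours in bed at home, and the fixed 8 AM wake time removes one of them.

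What is at stake is next-morning sedation. Study Medication names somnolence as the drug's most common adverse effect, and these participants are asked to complete a trauma-writing session that morning.

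**Working it through.** **Inputs.** Latest eligible bedtime 2 AM (exclusion 8); wake time 8 AM (Sleep recordings); dose 0.5 h before bedtime, on at most two nights (Study Medication Administration); cited minimum 7 h in bed (Study Medication). The plan states no time in bed, so there is no figure of its own to reproduce.

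**Formulas.** Time in bed = 8:00 − bedtime. Dose to wake = time in bed + 0.5 h.

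| Usual bedtime | Time in bed | Short of 7 h by | Dose to wake | Short of 7 h by |
|---|---|---|---|---|
| 12:00 AM | 8.0 h | none | 8.5 h | none |
| 1:00 AM | 7.0 h | none | 7.5 h | none |
| 1:30 AM | 6.5 h | 0.5 h | 7.0 h | none |
| 2:00 AM | 6.0 h | 1.0 h | 6.5 h | 0.5 h |

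The cited wording concerns staying in bed, so the time-in-bed column is the natural reading. On that reading the threshold is 1 AM, and the full one-hour shortfall occurs only at 2 AM. Counted from the dose, the threshold moves to 1:30 AM and the largest shortfall is 30 minutes.

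**How many people.** The share s with bedtimes after 1 AM is not in the documents. The Feasibility section gives two counts: about 70 who complete at least the first two writing sessions, and 54 who complete everything (27 per group). Assuming an equal split of the 70:

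- First dosing night: 35s on suvorexant. An assumed s of 0% to 20% gives 0 to 7.
- Second dosing night: 27s on suvorexant. The same range gives 0 to 5.4.

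These figures show scale only. Dosing follows session 1, so someone dosed who then misses session 2 is not among the 70. Someone dosed twice who misses the final follow-up is not among the 54. Neither count is an upper limit on the number dosed.

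**Check of the scheduling rules.**

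- Wake at max(8:00, bedtime + 7 h): 8:00, 8:30 and 9:00 for bedtimes of 1:00, 1:30 and 2:00. Time in bed is 7.0 h in each case. From the 8 PM session start to waking is 12, 12.5 and 13 h.
- Bedtime at min(usual, 1 AM) with waking at 8 AM: at least 7.0 h for everyone, and session times do not move.

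**The case against.** The strongest reply is that little is left once the safeguards are counted. The first dose is the recommended 10 mg, given in a research unit with nurses at hand. Only people who tolerated it on the same schedule go to 20 mg. The morning session waits for alertness, and drowsy participants may not drive.

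The one harm rate in the Protocol also points to small numbers. Somnolence was 7% against 3% on placebo with 20/15 mg taken daily for three months. A 4-point excess applied to the illustrative 7 people is 7 × 0.04 = 0.28 cases. In addition, the 9 AM limit on usual rise times means that the study night can cut a 2 AM sleeper's usual time in bed by at most one hour, and someone who usually rises at 8 AM loses nothing.

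All of this stands as a limit on size. It does not close the gap:

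- None of the safeguards restores time in bed.
- The tolerance rule cannot act before the first dose.
- The reference level for alertness is taken after a baseline night that was equally short for these participants, so it may itself be low.
- The 0.28 rests on an assumed share and a completer count, and the documents do not say what a shorter night adds to the somnolence rate.

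A reader might infer that the Protocol contradicts itself. It does not: it reports the seven-hour instruction as the manufacturer's and never adopts it as a study rule. This is a departure from cited guidance without a stated reason.

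**Conclusion.** The point holds as a minor safety improvement. As written, the schedule gives anyone with a bedtime after 1 AM and up to 2 AM 6.0 to under 7.0 hours in bed on one or two dosing nights. The shortfall is at most one hour, or at most 30 minutes if time is counted from the dose. This rests only on clock arithmetic and on participants keeping the instructed times.

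The number affected is unknown and may be zero. The 0% to 20% range is an assumption with no source in the documents.

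A reader might also infer biased sleep or symptom results. The documents do not support that, because both arms follow the same bedtimes and wake time and the baseline night is on the same schedule. Nor do they show that any participant would come to harm.

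**What to change.** Guarantee at least seven hours in bed by a scheduling rule on all sleep-recording nights. Baseline must be included, because sleep change is calculated by subtracting the baseline night. Either rule works:

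1. **Later waking.** Wake at the later of 8 AM and bedtime plus 7 h, so 9 AM at the latest, with the morning session following. This means amending the 8 AM times in Design and Overview, Sleep recordings and Written Narrative Exposure. It moves the session by up to one hour for a few people, which varies clock time and the interval between sessions in the habituation analysis. The Pulse rate section already treats circadian influence as a concern. However, the start time is only approximate and already waits for alertness, so the plan largely accommodates this. Some participants may spend longer in bed than usual, which could affect wake after sleep onset (WASO).
2. **Earlier bedtime.** Go to bed at the earlier of the usual time and 1 AM. Session times stay fixed. The cost is a bedtime up to one hour earlier than usual for a few people. Dose timing must then be tied to the scheduled bedtime: a usual 2 AM sleeper would otherwise be due a tablet at 1:30 AM, after going to bed at 1 AM.

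Lowering the exclusion limit to 1 AM is a fallback only, for use if the screening sleep questionnaire shows that few people would be lost. The SAP's power section needs 50 participants for REM percentage and expects 54. Without replacement, 54(1 − s) ≥ 50 requires s ≤ 4/54 = 7.4%. A 10% loss leaves 48.6, and 20% leaves 43.2.

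If the shorter night is intended, one sentence of rationale should say so.
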